1.4 Study Population

The main study will enroll 300 subjects ranging from ages 18 to 75, who are diagnosed with Major Depressive Disorder (without psychosis).

The add-on Exploratory Elderly MDD Study will randomize 70 subjects age 65 years and older.

Subjects will be recruited from psychiatric outpatient clinics.

Elderly MDD study subjects will begin randomization after enrollment for the primary study has been completed.

1.5 Risk/Benefit Assessment

- 1. Subjects will have full access to appropriate pharmacotherapy at all times since they will be receiving approved psychotropic drugs with proven efficacy and acceptable safety. It is possible, however, that the test results could cause the treating investigator to choose a less effective treatment regimen than would otherwise have been selected, or that the selected treatment regimen may be associated with problematic adverse effects. This will be clearly explained to all subjects in the informed consent form.
- 2. Delay in treatment: By participating in this study, subjects are likely to experience a delay in initiation of active treatment during the time needed for completion of genotyping by the study laboratory and review of these results by the treating investigator. This may delay treatment by up to 7 days but no greater than 12 days. During this period, it is possible that the subject's condition could worsen. The following steps, however, will be implemented to minimize risk to the subject:
 - A) If needed, the investigational site will give the subject opportunity to maintain contact with the investigator and site throughout the waiting period so that the subject's psychiatric status can be monitored. Subjects will be provided with study-specific contact information and a phone contact to the subject by the site will be made as indicated midway between Screening and Day 0.
 - B) Pending results of the genetic test, subjects who are taking psychotropic medications at the time of enrollment will continue to take the same medications, as per the treating investigator's clinical judgment.
 - C) Subjects currently taking psychotropic medications or subjects not taking psychotropic medication at screening who are in need of immediate change or addition of pharmacotherapy may receive this from the treating investigator as clinically indicated. These patients will not be eligible for enrollment/randomization at that time but may be eligible (for one time only) for re-screening at a later point during the enrollment period of the study (\geq 6 weeks).

- 3. During the course of the assessments of the subject, unexpected information on the subject's psychiatric or medical condition may emerge. Should this occur, this information will be discussed with the subject.
- 4. During the clinical interviews, the subject may become fatigued or distressed from the questions. If this occurs, he/she should communicate this to the interviewer/study personnel and the assessment will be stopped. The subject will be given a break period or rescheduled.
- 5. Genetic study: Variation in some genes has been associated with risk for various medical or psychiatric illnesses. If confidentiality were to be breached unexpectedly, despite adherence to federal GINA laws, the subject could be jeopardized with respect to insurability or employment, for example. Genetic information from this study will not be disclosed to insurers or other organizations without the written permission from the subject, as applicable by governing laws. Every effort will be made to maintain confidentiality for all subjects, as per federal and institutional requirements.
- 6. Subjects may experience improvement in psychiatric symptoms, and the study data obtained may provide information about treatment strategies for psychiatric disorders in the future. Depression remains a major clinical problem despite availability of multiple effective treatments. This study may validate a test to facilitate more rapid selection of treatments that may prove optimal with respect to efficacy and safety in a given subject.
- 7. Subjects may request a copy of the Genecept Assay TM report at the Week 8 visit after all visit and study assessments have been completed or 8 weeks after randomization for subjects that discontinued early.

2 HYPOTHESIS AND STUDY OBJECTIVE

2.1 Study Objective

To assess the efficacy of assay-guided treatment (AGT) versus treatment-as-usual (TAU) in subjects with MDD at 8 weeks. Additionally, to assess the efficacy and safety of assay-guided treatment (AGT) versus treatment-as-usual (TAU) in subjects with MDD at 8 weeks in subjects age 65 years old and older, a separate analysis will be performed on the approximately 70 subjects in the add-on Elderly MDD Study.

2.2 Clinical Hypothesis

Compared to treatment-as-usual, pharmacological interventions in the treatment of major depressive disorder that are guided by the Genecept Assay TM will be more effective in reducing depressive severity and medication-induced side effects.

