The primary endpoint (change from baseline in SIGH-D-17) analysis will be performed using the MMRM method in the FAS population. The model will include the fixed effect continuous factor baseline SIGH-D-17, and fixed effect categorical factors investigative site, treatment group (AGT and TAU; 2 levels), visit (Weeks 2, 4, 6 and 8; 4 levels), and treatment x visit interaction.

AGT and TAU mean change in SIGH-D-17 at Week 8 will be estimated and tested utilizing the least squares (LS) means from the treatment x visit interaction in the MMRM model. The primary analysis will test the difference (contrast) between the Week 8 least squares (LS) means, at two-sided significance 0.05. The test p-value and the 95% CI for the difference in Week 8 means will be presented. Comparisons between the AGT and TAU means at Week 2, Week 4 and Week 6 will also be generated.

Key continuous secondary endpoints will be analyzed using the same MMRM model as for the primary endpoint.

Key categorical secondary endpoints will be analyzed using the Mantel-Haenszel method, stratified on pooled site.

The remaining efficacy and safety data will be summarized by treatment group using descriptive statistics and frequency tables.

Subgroup Analyses:

Consistency of AGT vs TAU treatment effect on SIGH-D-17 will be assessed across various subgroup factors described below, by evaluating the treatment by subgroup interaction in the MMRM model.

 Subgroup factor
 Subgroup categorization

 Age group
 < median age, ≥ median age	Gender Male, Female Race White, Non-white

Baseline SIGH-D-17 $< 24, \ge 24$ Investigative Site Pooled

Statistical Methods (Exploratory Elderly MDD Study) The primary efficacy endpoint (change from baseline in SIGH-D-17) analysis will be performed using a Last Observation Carried Forward Analysis of Covariance, in FAS population.

Generally, the statistical methods for the Exploratory Elderly MDD Study will follow the outline of the Main Study, but will be primarily descriptive, and statistical analyses will be simpler, as necessitated by the much smaller sample size. The SAP for the Elderly MDD Study, incorporated in the overall SAP (V 3.0), will detail the statistical approaches to be used. The SAP (V 3.0) will be finalized and approved before the Elderly Study database is unblinded.

Sample Size Computations

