6.4.5 Missing Visits

Investigators should minimize the occurrence of missed study visits. Flexibility of scheduling visits within protocol windows and good communication with subjects (e.g., providing a predicted visit schedule, reminder calls or emails, etc.) are to be implemented. In case of missed visits, reason for the missed visit must be documented in the eCRF.

6.5 Screen Failures

If subjects do not meet inclusion criteria or meet exclusion criteria at any time prior to randomization, they will be considered screen failures. Screen failures must be registered in IWRS; demographic information and reason(s) for screen failure (record all applicable reasons) must be recorded. In select cases, a screen failure subject might be eligible for re-screening at a later point (\geq 6 weeks) during the study, for one time only, after approval by the study sponsor has been obtained.

Early Discontinuation and Potential Missing Data Remediation

Subjects may voluntarily withdraw from the study at any time. Early discontinuation must be registered in IWRS; reason for early discontinuation must be obtained and recorded in the eCRF. If feasible, the investigator should make his/her best efforts to have the subject return for Week 8 study assessments.

At a minimum, Week 8 SIGH-D-17 assessment, C-SSRS assessment and adverse event collection should be attempted. To maintain blinding, the disclosure of treatment group and discussion of assay results will only occur at the Week 8 visit or 8 weeks after randomization for subjects that discontinued early.

6.7 Early Termination of Study

The study may be terminated by the site investigator at his/her study site at any time. Genomind may terminate the study (and/or the study site) for any reason with appropriate notification.

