6.8 Safety Evaluation

Safety measures will include adverse event collection and C-SSRS administration at all visits, and medication side effect reporting collected by FIBSER and PRISE at Baseline (Day 0), Week 2, 4, 6 and 8 visits and at any unscheduled visits or during other contacts with the subject, as applicable.

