9.5 Safety Analyses

All safety analyses will be performed on the SAF dataset.

Adverse events

The analysis will focus on the TEAEs. TEAEs will be summarized and tabulated according to body system and frequency for each treatment group. Separate tabulations of AEs depending on seriousness, severity, possible relationship to study medication, and outcome "death" will be given.

• FIBSER, PRISE

The results from the FIBSER and PRISE scales will be summarized descriptively.

Note: Safety data for the MDD Elderly MDD Study will be descriptively summarized in the SAF.

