9.8 Sample Size Justification

Sample size is calculated for the primary endpoint, improvement from baseline to eight weeks in the SIGH-D-17 of subjects with Major Depressive Disease.

As there are few studies comparing MDD AGT vs TAU, information to guide sample size is limited.

Nevertheless, three controlled MDD trials of AGT vs TAU⁴⁹⁻⁵¹provide some quantitative basis for sample size. All are single center, 8-10 weeks in duration, measured SIGH-D-17, and utilized the AssureRx assay battery. For each study an approximate SIGH-D-17 Delta and SD were approximated from tables and figures in the report publication. Delta is the between group difference in mean SIGH-D-17 change and SD is the assumed constant standard deviation of the individual subject's change in HAMD). Cohen's d = Delta/SD was further calculated. Brief summaries of the three studies follow:

- 1) Hall-Flavin DK et al 2012, *Using a pharmacogenomic algorithm to guide the treatment of depression*⁴⁹. This was the pilot study for next trial in this list: non-randomized, open, single center, comparison of pharmacogenomic guided treatment vs usual treatment for 8 weeks. N=51, 44 analyzed. Dropout rate = 14%. Approximate Delta and SD = 3.5 and 6.0. Approximate delta/SD ratio= 0.58
- 2) Hall-Flavin DK et al 2013.Utility of integrated pharmacogenomic testing to support the treatment of major depressive disorder in a psychiatric outpatient setting⁵⁰. Non-randomized, open, single center, comparison of pharmacogenomic guided treatment vs usual treatment for 8 weeks. N=227, 165 analyzed. The dropout rate = (27%) with 37% AGT vs 18% TAU dropout. The approximate delta and SD are 3.1 and 7.2. Approximate delta/SD ratio= 0.43
- 3) Winner JG et al 2013.A prospective, randomized, double-blind study assessing the clinical impact of integrated pharmacogenomic testing for major depressive disorder⁵¹. Pilot study, randomized, single center, blinded subject and rater, comparison of pharmacogenomic guided treatment vs usual treatment for 10 weeks. (Although described as double-blind, the Winner study does not meet the minimum conventional double-blind standard blinded investigator and subject) N=51, 49 analyzed. The approximate Week 8 delta/SD ratio=0.47. This ratio was extrapolated from the % SIGH-D-17 improvement results, and is likely an overestimate of the mean SIGH-D-17 improvement ratio.

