#### Secondary Objectives

- To assess efficacy of assay-guided treatment (AGT) versus treatment-as-usual (TAU) in Major Depressive Disorder, as measured by change in Quick Inventory of Depressive Symptoms (QIDS-SR16) at 8 weeks.
- To assess the percentage of responders at Week 8, based on SIGH-D-17, QIDS-SR16, and Clinical Global Impression–Improvement (CGI-I), respectively. Treatment response will be defined in 3 different ways:
  - Blinded Rater Assessment: ≥ 50% reduction from baseline of SIGH-D-17 score ;
  - Subject-Rated Assessment: ≥ 50% reduction from baseline of QIDS-SR16;
  - Unblinded Clinician Assessment: ≤ 3 score on the CGI-I;
- To assess the percentage of remitters at Week 8, based on the SIGH-D-17 and QIDS-SR16, respectively. Remission is defined for the SIGH-D-17 and the QIDS-SR16:
  - Blinded Rater Assessment: ≤ 7 score on the SIGH-D-17;
  - Subject-Rated Assessment: ≤ 5 score on the QIDS-SR16
- To assess the impact of the Genecept Assay ™ on adverse events, based on Frequency, Intensity and Burden of Side Effects Rating (FIBSER) and Patient-Related Inventory of Side Effects (PRISE), frequency and severity of adverse events and Columbia-Suicide Severity Rating Scale (C-SSRS) outcomes.
- After completion of the main MDD study, to conduct the Exploratory Elderly MDD Study, to preliminarily assess the efficacy and safety of AGT vs TAU in the elderly, age  $\geq$  65. This study will provide additional data on this important, Medicare-eligible population, which is sparsely represented in the Main Study (< 8% of subjects). As specified in Protocol Amendment 2, after the Main Study enrollment finishes, approximately 70 subjects, age  $\geq$  65, will be randomized to the this add-on study. Except for change in age of inclusion, all study procedures will be identical to the Main Study. Primary efficacy will be measured by change in Hamilton Depression Rating Scale (SIGH-D-17) at 8 weeks.

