#### 3.5 Safety Analyses

**Note:** This section applies to both the Main Study and the Exploratory Elderly MDD Study, although safety analyses may be adjusted in the Exploratory Elderly MDD Study to reflect sparse sample sizes, eg, substitution of a short listing in place of a full table.

All safety analyses will be performed on the SAF dataset.

• Adverse events

The analysis will focus on the TEAEs. TEAEs will consist of all AEs with start date after Baseline. Continuing pre-Baseline AEs which worsen in severity or seriousness will be reported in the CRF as new AEs, and thus will be TEAEs. TEAEs will be summarized and tabulated according to body system and frequency for each treatment group. Separate tabulations of AEs depending on seriousness, severity, relationship to MDD treatment, action taken and outcome will be given. SAEs will be correspondingly summarized.

• FIBSER and PRISE

Overall and by visit results from the FIBSER and PRISE scales will be summarized descriptively by treatment.

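### Side effects are part of the clinical hypothesis and a secondary objective, but no AGT-versus-TAU estimate or confidence interval is planned for them

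*Protocol*

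**What the plan says.** **Hypothesis and objective.** Protocol 2.2 states that treatment guided by the assay "will be more effective in reducing depressive severity and medication-induced side effects" than treatment-as-usual. That sentence is directional, compares the arms, and covers both outcomes. The Protocol Summary and SAP 1.3 list as a secondary objective the assay's impact "on adverse events, based on Frequency, Intensity and Burden of Side Effects Rating (FIBSER) and Patient-Related Inventory of Side Effects (PRISE"), and go on to name adverse event frequency and severity and C-SSRS outcomes.

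**Analysis.** Protocol 9.5: "The results from the FIBSER and PRISE scales will be summarized descriptively". SAP 3.5: "Overall and by visit results from the FIBSER and PRISE scales will be summarized descriptively by treatment". TEAEs are tabulated by body system and frequency within each arm. The Protocol Summary sets the general rule: "The remaining efficacy and safety data will be summarized by treatment group using descriptive statistics and frequency tables".

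**Collection.** Protocol 6.8 provides for "medication side effect reporting collected by FIBSER and PRISE at Baseline (Day 0), Week 2, 4, 6 and 8 visits", and also at unscheduled visits and other contacts as applicable. For early discontinuers, Protocol section 6 (Early Discontinuation and Potential Missing Data Remediation) asks the investigator to try to bring the subject back for the Week 8 assessments. As a minimum, "Week 8 SIGH-D-17 assessment, C-SSRS assessment and adverse event collection should be attempted"; FIBSER and PRISE are not in that minimum.

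**The concern.** Whether AGT reduces side effects is a question about the difference between arms. The depression half of the same hypothesis gets MMRM contrasts with a 95% CI, and Mantel-Haenszel odds ratios with CIs for response and remission. The side-effect half gets separate by-arm summaries, with no effect measure or planned interval.

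Description by arm is normal for routine safety monitoring. Here, however, lower side-effect burden is a claimed benefit of the test. Without a named contrast, any statement about it in the report would rest on comparing two columns by eye, or on a contrast chosen after the data are seen.

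A Week 8 difference taken from the tables would also ignore baseline FIBSER, although it is collected, and would include only subjects with a Week 8 FIBSER. No missing-data handling is stated for that scale. If subjects troubled by side effects leave more often from one arm, the crude difference is distorted.

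**Working it through.** **1. The plan's own figure.** Inputs from Protocol 9.8: delta 3.1, SD 7.2, two-sided alpha 0.05, power 90%, dropout 23%.
- Normal approximation: n = 2(1.960 + 1.282)² × (7.2/3.1)² = 113.4, so 114 per arm.
- The t-test version gives 114.3 (d = 3.1/7.2) to 114.6 (d = 0.43), so 115.
- 115/(1 − 0.23) = 149.4, so 150 per arm.

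The stated 115 and 150 reproduce. They concern SIGH-D-17 only; the documents give no effect size, SD or precision for any side-effect measure.

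**2. Precision of a FIBSER contrast, in SD units.** Half-width = t(0.975, 2n − 2) × √(2/n), before covariate adjustment. The detectable difference uses the noncentral t at two-sided 0.05 and 80% power.

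| Missing at Week 8 | n per arm | 95% CI half-width | Detectable difference |
|---|---|---|---|
| 23% | 115 | 1.970 × 0.1319 = 0.260 | 0.371 |
| 10% | 135 | 1.969 × 0.1217 = 0.240 | 0.342 |
| 0% | 150 | 1.968 × 0.1155 = 0.227 | 0.325 |

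Baseline adjustment multiplies the half-width by √(1 − r²). For an assumed baseline-to-Week 8 correlation of 0.3, 0.5 or 0.7, the 0.260 falls to 0.248, 0.225 or 0.186.

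**3. Precision of a TEAE risk difference.** Half-width = 1.96 × √(2p(1 − p)/n). The documents give no TEAE rates, so p is assumed to be 20%, 40% or 60%.
- 150 per arm: 9.1, 11.1 and 11.1 percentage points.
- 115 per arm: 10.3, 12.7 and 12.7 percentage points.

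**4. Error of the crude Week 8 difference when the true difference is zero.** By simulation, 400,000 subjects per arm:
- baseline plus four visits, SD 1, common correlation rho, higher score taken as worse;
- dropout after Weeks 2, 4 and 6, with logit slope b on the last observed score.

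All of these are assumptions. With dropout set to the reference study's split, "with 37% AGT vs 18% TAU dropout", the crude AGT minus TAU difference is:

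| rho | b = 0.5 | b = 1.0 | b = 1.5 |
|---|---|---|---|
| 0.4 | −0.043 | −0.074 | −0.095 |
| 0.6 | −0.067 | −0.109 | −0.135 |
| 0.8 | −0.089 | −0.147 | −0.181 |

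Other dropout splits:
- Protocol 9.8 calls 10% dropout realistic. A similar split at that level (13.5% versus 6.5%, mean 10%) gives errors of about 0.01 to 0.07 SD across the same grid.
- At rho = 0.6 and b = 1.0, 28% versus 18% gives −0.056, 23% versus 23% gives 0.001, and 18% versus 37% gives +0.111.

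A likelihood (MMRM-type) estimate stays within 0.003 of zero in all nine cells of the table. That follows from the set-up, because simulated dropout depends only on observed scores. It does not show that MMRM would be unbiased in the trial.

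**The case against.** **Descriptive safety analysis is a declared and consistent choice.** Every analysis section says the same, Protocol 2.1 names only efficacy for the Main Study, the secondary objective is neutrally worded, and these measures sit under safety endpoints. This stands as far as it goes: the direction comes from Protocol 2.2 alone. It does not remove the gap, because that hypothesis and the secondary objective both concern the assay's effect. Narrowing 2.2 would remove the directional mismatch but leave the objective without an estimate.

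**The planned tables allow a contrast.** SAP 3.5 gives overall as well as by-visit summaries. Protocol 8.1 and SAP section 2 promise n, mean and SD or standard error for continuous variables, and TEAE counts by arm in the SAF yield a risk difference. This is correct. A reader might infer that the side-effect question cannot be addressed from the planned output; the documents do not support that.

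**Early leavers are not lost.** A reader might infer that subjects who stop early contribute no side-effect data. They contribute earlier visits, their return for Week 8 is to be attempted, side effects can be recorded at other contacts, and adverse events are in the minimum set. What stands is narrower: FIBSER is not in that minimum.

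**The 37% versus 18% split is borrowed.** It comes from an open, non-randomised, single-centre study of a different assay battery, and the documents do not say why its arms differed. It can serve only as an upper scenario.

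**FIBSER scoring is not documented.** Protocol 19.1 describes three patient-rated questions without range or direction. A normal-theory model on one item therefore needs a stated scoring rule and diagnostics.

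**Conclusion.** The point holds in a limited form. A side-effect benefit is hypothesised and its assessment is a secondary objective, but no between-arm estimate or interval is planned. A crude contrast can be derived, but it would not be adjusted for baseline and has no missing-data rule.

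Its possible error is modest near the plan's 10% dropout target: about 0.01 to 0.07 SD, against a half-width of 0.24 SD. It reaches 0.18 SD only in the borrowed 37% versus 18% scenario with the strongest assumed dependence. It is zero with equal dropout and reverses if TAU loses more. A reader might conclude that the plan favours AGT on side effects; nothing in the documents establishes that, because the direction depends on a dropout pattern that they do not give for this trial.

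The existing sample gives usable precision (0.23 to 0.26 SD), so no change in size is needed. The primary efficacy test is unaffected. The change is worth making, but the trial's validity does not depend on it.

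**What to change.** In Protocol 9.5 and SAP 3.5, for the Main Study:

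- Name one lead side-effect measure, for example the FIBSER burden item. It is rated by subjects, who are blinded, whereas adverse event severity is rated by the unblinded treating investigator (Protocol 3.3 and 7.1.2). State its scoring direction.
- Report the Week 8 AGT minus TAU LS-mean difference with 95% CI in SAF subjects with a post-baseline FIBSER. Use the primary MMRM terms and visit windows, with baseline FIBSER burden replacing baseline SIGH-D-17, and check the model diagnostics.
- Report the unadjusted AGT minus TAU risk difference, with 95% CI, for subjects with at least one TEAE.
- Label both as supportive and not multiplicity-controlled. The other FIBSER items, PRISE and the Elderly Study safety data may stay descriptive.

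The cost is an amendment to two sections and a little extra analysis of data already scheduled. The result is not confirmatory, and MMRM still assumes that dropout depends only on observed data.

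SAP 1.1 refers to Main Study unblinding in the past tense, which suggests but does not state that it has happened. If it has, report both analyses in the CSR as post-unblinding, the route that Protocol 8.1 provides.
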